#### 10.7.5. Sensitivity analyses

If the primary analysis demonstrates favourability towards Chronocort®, sensitivity analyses will be performed using different definitions of the SDS to check the robustness of the result.

## 11. Safety analyses

### 11.1. Extent of exposure

Summary statistics will be presented for both the total duration and actual duration of exposure in days. Total treatment duration will be calculated as follows:

Date of first dose of study drug – Date of last dose of study drug + 1.

Actual treatment duration will consider dose interruptions and will be the total number of days in which the subject took at least one dose of study medication.

The recommended dose titrations which are made by a central independent blinded physician within 2 weeks of each profiling visit will be summarised by treatment group for week 4 and week 12. The summary will show frequency and percentage of subjects requiring a dose adjustment, as well as the dose adjustment required (for both treatment groups: increase morning dose, increase evening dose, decrease morning dose, decrease evening dose; and additional doses for standard GC therapy: increase middle dose, decrease middle dose). A listing of dose titration decisions which are contrary to those directed by the blinded physician will be produced showing the reason for the deviation.

A summary of unplanned dose changes will be produced showing the number of increases and decreases in dose that were unplanned i.e. not at the scheduled timepoints.

A summary of the number and percentage of subjects with dose increases, reductions and interruptions will be produced also showing the number of dose increases, reductions and interruptions per subject, and summary of reason for dose increases, reductions and interruptions.

All treatment exposure data will be listed in detail. In addition to this, the study drug dosing instructions given to the subject by the investigator will be listed in detail.

### 11.2. Adverse events

All AEs, in terms of MedDRA system organ class (SOC) and preferred term (PT), will be listed and summarised descriptively by count (n) and percentage (%) for each treatment group. For the purpose of the CSR, only AEs up to the follow up-telephone call after the week 24 visit will be included in summaries. Any AE occurring before randomised Chronocort®/ standard glucocorticoid replacement therapy treatment (i.e. before the first dose of randomised treatment on Day 2 of visit 1) will be included in listings but not summaries, unless there is an increase in severity occurring after the start of treatment. Similarly, any AE occurring after the last day of study treatment for subjects who enter the extension study or the last day of study treatment plus 30 days for subjects who do not enter the extension study will be listed but not summarised.

All reported AEs will be listed along with the study day of onset, resolution, duration, seriousness, severity, action taken with study drug, relationship to study drug, treatments administered and outcome. Frequencies and percentages of subjects reporting each PT will be presented (i.e. multiple events per subject will not be accounted for, apart from on the episode level summaries). Where severity is displayed, if a subject has more than one AE of the same term, the maximum severity will be used.

An overview table of AEs displaying the number of AEs by treatment group as well as the number and percent of subjects with the following categories will be produced:

- Any AE
- Any AE causally related to IMP

- Any AE leading to sick day rules
- Any AE leading to sick day rules causally related to IMP
- Any AE leading to Addisonian crisis
- Any AE leading to Addisonian crisis causally related to IMP
- Any AE leading to unexpected therapeutic benefit
- Any AE leading to unexpected therapeutic benefit causally related to IMP
- Any AE leading to death
- Any AE leading to death causally related to IMP
- Any AE leading to discontinuation
- Any AE leading to discontinuation causally related to IMP
- Any SAE
- Any SAE causally related to IMP
- Any SAE leading to discontinuation
- Any SAE leading to discontinuation causally related to IMP.

The number and percent of subjects experiencing each AE will be summarised by treatment, SOC and PT for the following:

- All AEs
- All serious adverse events (SAEs)
- SAEs with outcome of death
- AEs leading to discontinuation of study treatment
- SAEs leading to discontinuation of study treatment

Separate summaries for AEs and SAEs will be created, split by the following:

- Causality (not related, related to the investigational medicinal product (IMP), related to sick day medication, related to an interaction between IMP and sick day medication, related to either IMP or sick day medication)
- Action taken (dose unchanged, dose increased, dose decreased, drug interrupted, drug withdrawn)
- Outcome (Resolved, resolved with sequelae, resolving, not resolved, unknown, fatal)
- By severity (Mild, moderate, severe)

Additionally, all summaries above have the potential to be repeated to show the number of episodes in each category (using total number of patient-years exposed to IMP as the denominator). This is optional and to be done only if there are differences in exposure between treatment groups. A decision as to whether this is required will be made at the Data Review Meeting.

Tables of most common AEs (frequency of >10%) and common SAEs (>1% of subjects overall), will be summarised by preferred term, by decreasing frequency. These thresholds may be adjusted downwards at the Data Review Meeting if there are relatively few subjects with AEs.

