6. ECG
7. the incidence, nature, severity, relatedness, duration, outcome and seriousness of treatment emergent AEs
8. the incidence, nature, severity, relatedness, duration, outcome and seriousness of 'sick days' and Addisonian crises.

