### 13.7 Safety Analysis

Safety variables, will be listed and summarised by treatment, stratum and timepoint.

The nature, severity, relatedness, duration, outcome and seriousness and outcome of all AEs will be listed. The subject incidence of treatment emergent AEs will be tabulated by system organ class, preferred term, severity and relatedness. Tables will be provided of AEs of special interest, SAEs, SUSARs, AEs leading to withdrawal and fatal AEs.

Shift tables will be presented for laboratory variables and vital signs. Abnormal findings on physical examination and from ECG will be tabulated. Listings of laboratory data, vital signs, physical examination and ECG will have abnormal findings marked, together with an indication of whether or not that finding was clinically significant.

The versions of the following international dictionaries current at the time of study conduct will be used for medical coding:

- Diagnoses: MedDRA
- Medications: WHO Drug Dictionary including ATC classification
- Adverse events: MedDRA

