### Protocol Version 4.0 dated 28 May 2016

The following changes were made to the protocol:

- 1) The Sponsor signatory was changed from [REDACTED].
- 2) Different clinicians use different conversion factors for dexamethasone to hydrocortisone. The protocol states that 'The initial dose setting at the start of Chronocort® treatment will be made on hydrocortisone dose equivalent of baseline therapy, with the hydrocortisone dose calculated as dexamethasone dose multiplied by 80'. Investigators and Diurnal have been concerned that this may lead to a safety issue that if patients on a higher dose of dexamethasone were converted by x80 they would be exposed to excess hydrocortisone, therefore a greater mineralocorticoid effect, and be at risk of being overdosed. Therefore the protocol was amended to state that the current conversion rate of x80 should be used as per protocol up to a maximum starting dose of Chronocort® 30mg (split 20mg at night and 10mg in the morning). The justification for the maximum of 30mg Chronocort® is based on the fact this was the starting dose for all patients in the Phase 2 study (DIUR-003) (Mallappa 2015) and is in line with recommendations for hydrocortisone dosing in CAH (Speiser 2010). If the investigator has any concerns regarding the starting dose in a patient then these can be discussed with the Medical Monitor.
- 3) The protocol stated that blood samples should be taken for genotyping, unless genotyping had previously been performed. It was clarified that if previous genotyping had been performed the patient has to be asked for their permission for this information to be taken from their medical records.

- 4) Subjects who routinely work night shifts and so do not sleep during the usual nighttime hours was added to the exclusion criteria.
- 5) At the request of the Dutch ethics committee, the following sentence has been added to the procedures for the screening visit (Section 11.1.1) and also in Section 11.4 (Informed Consent): At Dutch centres only, potential subjects will be approached by their own treating physician. If the treating physician is also the investigator the subject information sheet can be provided immediately. If this is not the case then the treating physician will ask the patient for permission for the investigator to approach them about study participation.

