### 11.3. Adverse events of special interest

#### 11.3.1. Use of “sick days”

As per the protocol each site will have a set of sick day rules where certain AEs will result in emergency hydrocortisone being taken.

All AEs leading to use of “sick day rules” will be summarised (frequency and percentage of subjects) by system organ class, preferred term and treatment group.

In addition, all AEs leading to use of “sick day rules” will also be summarised (frequency and percentage of subjects) by preferred term, route of, and specific sick day medication by treatment group.

There will be a separate listing showing details of all AEs leading to use of sick day rules and specific sick day medication.

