#### 11.3.2. Adrenal crises

All AEs leading to adrenal crises as defined in the protocol will be summarised (frequency and percentage of subjects) by SOC, PT and treatment group. There will be a separate listing showing details of all AEs leading to adrenal crises.

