#### 11.7.4. Adrenal insufficiency

Signs and symptoms of adrenal insufficiency will be summarised by treatment group and visit. A listing of all signs and symptoms of adrenal insufficiency will be produced flagging any significant findings and significant findings related to under/over replacement of steroid.

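### The SAP summarises adverse events, sick days and adrenal crises by treatment group only, although the protocol commits to a split by stratum, and does not record the change

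*SAP*

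**What the plan says.** Protocol 13.7 opens with a general rule: "Safety variables, will be listed and summarised by treatment, stratum and timepoint". Protocol 13.3.5 lists eight safety variables. Item 7 is "the incidence, nature, severity, relatedness, duration, outcome and seriousness of treatment emergent AEs" and item 8 is "the incidence, nature, severity, relatedness, duration, outcome and seriousness of 'sick days' and Addisonian crises". The strata are the three prior-therapy groups used for randomisation: hydrocortisone only, prednisone or prednisolone, and dexamethasone (Protocol 8; SAP 8.4).

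The SAP gives these two items by treatment arm alone:

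- SAP 11.2: AEs are "summarised descriptively by count (n) and percentage (%) for each treatment group".
- SAP 11.3.1: AEs leading to sick-day rules are summarised "by system organ class, preferred term and treatment group".
- SAP 11.3.2: AEs leading to adrenal crises are "summarised (frequency and percentage of subjects) by SOC, PT and treatment group".

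The planned tables in SAP 14.1 include no AE table split by prior therapy. SAP 12, which lists departures from the protocol's analyses, mentions laboratory shift tables and the removal of dose-level splits for vital signs and abnormal ECG results. It says nothing about strata. The introduction to Protocol 13 allows minor changes of method without an amendment, but requires them to be documented in the SAP and in the study report.

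**The concern.** Stratum is the factor the trial randomises by, and what a Chronocort subject gives up differs between strata. Subjects from the prednisone/prednisolone and dexamethasone strata change their active drug, or part of it, as well as the formulation; hydrocortisone-only subjects stay on hydrocortisone. The protocol's amendment history (Appendix 10, Version 4.0) also records a concern that subjects on a higher dexamethasone dose, once converted, could be "exposed to excess hydrocortisone, therefore a greater mineralocorticoid effect, and be at risk of being overdosed". A harm could therefore be concentrated in one prior-therapy group.

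For efficacy, the protocol synopsis already asks for results within baseline treatment subgroups, so that non-hydrocortisone regimens do not account for the whole effect. The same reasoning applies to harm.

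If only pooled columns are produced, the report could describe AE, sick-day and crisis rates as similar between arms when that is not so for one stratum. The planned tables would not show it.

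**Working it through.** **Step 1: set the protocol's safety variables against the SAP's splits.**

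| Protocol 13.3.5 item | SAP section | Split by prior therapy? |
|---|---|---|
| 1. Weight, BMI, waist | 11.5 | Yes |
| 2. Haematology, clinical chemistry | 11.4.2, 11.4.3 | Yes |
| 3. Physical examination | 11.7.1 | Yes |
| 4. Vital signs | 11.5 | Yes |
| 5. Urinalysis | 11.4.4 | Yes |
| 6. ECG | 11.6 | No (treatment, visit, dose level) |
| 7. Treatment-emergent AEs | 11.2 | No |
| 8. Sick days, Addisonian crises | 11.3.1, 11.3.2 | No |

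Five of the eight items keep the split and three do not. SAP 12 declares none of the three omissions.

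**Step 2: what pooling does to an excess in one stratum.** The plan gives no figure on this point. Its only relevant number is the sample size, which reproduces: 102 / (1 − 0.15) = 120 randomised. No allocation ratio is stated. Assuming 1:1 gives 60 on Chronocort.

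Let f be the affected stratum's share of the Chronocort arm, h the event rate in it and b the rate elsewhere. Then:

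- pooled rate = f × h + (1 − f) × b
- pooled excess = pooled rate − b = f × (h − b)

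The excess therefore shrinks by the factor f. Stratum sizes and event rates are not in the documents, so all values of f, h and b below are assumptions.

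With b = 10% and h = 30% (a true excess of 20 points):

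| f | Subjects | Pooled rate | Pooled excess |
|---|---|---|---|
| 0.10 | 6 | 12% | 2 points |
| 0.20 | 12 | 14% | 4 points |
| 0.30 | 18 | 16% | 6 points |
| 0.50 | 30 | 20% | 10 points |

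With b = 5%:

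- f = 0.10, h = 25%: 0.10 × 25% + 0.90 × 5% = 7.0%
- f = 0.25, h = 40%: 0.25 × 40% + 0.75 × 5% = 13.75%

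**Step 3: what a by-stratum table could show.** Exact 95% intervals for rates near 30% are wide:

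- 2 of 6: 4% to 78%
- 4 of 12: 10% to 65%
- 5 of 18: 10% to 53%
- 9 of 30: 15% to 49%

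With no events, the upper limit is about 46% for 6 subjects and 22% for 15. Such tables can display a cluster of events, but they cannot establish or exclude a difference.

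**The case against.** The best defence is that the protocol does not clearly promise AE tables by stratum. The AE sentence in 13.7 names system organ class, preferred term, severity and relatedness, but not stratum. Section 13.1.1 names efficacy variables, vital signs and laboratory assessments for the stratum split, but not AEs. The synopsis relates AE rates to the subjects treated in each treatment group. The opening rule of 13.7 also says timepoint, which nobody would apply literally to AE tables. On this view the SAP simply follows the narrower text.

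The protocol could be clearer, but these texts do not displace the general rule. The AE sentence names no treatment split either, so it cannot be a full specification of the tables; it describes rows, and the opening sentence supplies the columns. Section 13.1.1 does not say that its list is exclusive, and the SAP itself splits physical examination, which 13.1.1 does not name. The synopsis sets a denominator and does not rule out a further breakdown. Timepoint fits variables measured at visits, whereas stratum is a property of the subject and applies to any variable.

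Two further points stand. The information is not lost: SAP 14.2 lists AEs, sick-day events and crises, and separately each subject's stratum, so rare crises can be read case by case, though only by linking listings by hand. And pooling dilutes an excess without necessarily hiding it: in the illustrations the pooled rate still lies above the background rate.

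**Conclusion.** The mismatch is real and undeclared. Protocol 13.7, read with 13.3.5, commits to by-stratum summaries of AEs, sick days and Addisonian crises, and the SAP neither plans them nor records their omission. An excess in one stratum would be diluted by that stratum's share of the arm. The amount cannot be derived from the documents; the 2 to 10 points shown above rest on assumed shares and event rates, and on 1:1 allocation.

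A reader might infer more than the documents support:

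- **That harms are expected mainly after dexamethasone or prednisolone.** Nothing says so. The only stratum-specific concern is the dexamethasone conversion in the amendment history, and the same amendment added a maximum starting dose. No such concern is recorded for prednisone or prednisolone. The Benefit/Risk Assessment in Protocol 5 expects risks similar to those of the subject's therapy at entry.
- **That hydrocortisone-only subjects change nothing but formulation.** Chronocort also fixes dosing times, while comparator dosing follows site practice (Protocol 10.3).
- **That AEs are the only exception.** ECG also lacks the split.
- **That SAP 7.1 confines subgroup summaries to efficacy.** It says where subgroup comparisons will appear and excludes nothing.
- **That the protocol promised adrenal-insufficiency symptoms by stratum.** SAP 11.7.4 states "Signs and symptoms of adrenal insufficiency will be summarised by treatment group and visit", but these symptoms are not among the 13.3.5 safety variables.

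**What to change.** In SAP 11.2, 11.3.1, 11.3.2 and 14.1, add descriptive tables (n, %) by treatment group within prior-therapy stratum for:

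- the AE overview;
- all AEs by system organ class and preferred term;
- SAEs;
- AEs leading to sick-day rules;
- AEs leading to adrenal crises.

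SAP Table 1 already defines the combined treatment and stratum columns. The signs-and-symptoms table in 11.7.4 could be repeated in the same way, as an addition to what the protocol asks. In SAP 12, record any by-stratum safety summary under Protocol 13.7 that is still omitted, such as ECG, with the reason.

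The cost is SAP wording and a few repeat tables from data already collected. No dosing rule or study procedure is affected. Cells in the smallest stratum may be small, so the tables should be labelled as descriptive, without tests.

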**Notes:**

1 Consent must be obtained prior to any study related procedures, including a DEXA scan (DEXA to be done everywhere except Germany)

2 Vital signs (blood pressure, heart rate, temperature)

3 If the subject has been receiving their normal medication for the previous 5 days (i.e. sick days rules have not been applied in the preceding 5 days) they will be admitted to the clinic for 24 hour endocrine profile (17-OHP and A4). If sick day rules have been applied in the previous 5 days then the 24-hour profiling should be postponed until subjects have been receiving their normal medication for 5 days. Samples to be taken at 15:00, 17:00, 19:00, 21:00, 23:00, 01:00, 03:00, 05:00, 07:00, 09:00, 11:00, 13:00, 15:00h. Exact times of sampling to be recorded in eCRF; samples to be taken within ±10 minutes of stated timepoints. If dosing is done at the same timepoints as the blood sampling, the blood sampling should be conducted first.

4 Plasma renin must be done at screening unless this has been done within 3 months of screening and documented in the patient notes.

5 DEXA is part of Baseline Visit 1 (except for Germany) but can be done up to 2 wks prior to baseline if scheduling difficult; consent must be taken prior to this study related procedure (applies only to Screening period).

6 Blood sample taken for genotyping, if possible, unless genotyping has previously been performed in which case the patient will be asked for their permission for this information to be taken from their medical records

7 Height, waist circumference & weight at first visit, only waist circumference & weight measured thereafter

8 First dose of study medication to be taken in evening of Baseline Visit 1 Day 2; dose adjustment must be done within 2 weeks of Visits 2 and 3.

9 Limited review of inclusion/exclusion criteria

10 The subject will receive clear written instructions of the dose they will be taking until the next study visit (even if there is no adjustment to be made) following the telephone call.

11 If the subject discontinues from the study early then as many assessments as possible should be completed

12 Only for subjects who do not enter the extension study

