The subject will return their medication (treatment pack 3 for subjects randomised to Chronocort®) and the number of capsules counted and recorded in the eCRF by the study team so compliance can be calculated (for both Chronocort® and the comparator). The safety pack should also be returned and checked, with any rescue medication use being recorded. An appointment will be made for the 30-day follow-up telephone call.

If the subject has completed the 24-week study period, they will then be eligible to take part in the extension study.

If the subject discontinues from the study early then as many of the above assessments as possible should be completed. Subjects who discontinue from the study early are not eligible to take part in the extension study.

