#### Safety

Duration of exposure (Safety analysis set)

Dose titrations recommended by the independent blinded physician (Safety analysis set)

Reasons for dose increases and reductions recommended by the independent blinded physician (Safety analysis set)

Table of dose titrations instructed by the Investigator (Safety analysis set)

Reasons for dose changes instructed by the Investigator (Safety analysis set)

Adverse event in any category - subject level (Safety analysis set)

Adverse event in any category - episode level (Safety analysis set)

Listing of deaths (Safety analysis set)

Adverse events leading to death (Safety analysis set)

Listing of adverse events leading to death (safety analysis set)

All adverse events (Safety analysis set)

All serious adverse events (Safety analysis set)

Listing of all serious adverse events (Safety analysis set)

Adverse events leading to discontinuation of study treatment (Safety analysis set)

Listing of adverse events leading to discontinuation of study treatment (Safety analysis set)

Adverse events by causality (Safety analysis set)

Adverse events by action taken (Safety analysis set)

Adverse events by outcome (Safety analysis set)

Adverse events by severity (Safety analysis set)

*Repeat above 6 tables for SAEs*

Most common (frequency of >10%) adverse events (Safety analysis set)

Most common (frequency of >1%) SAEs (Safety analysis set)

Adverse events leading to use of "sick day rules" (Safety analysis set)

Adverse events leading to use of “sick day rules” by sick day medication (Safety analysis set)

Adverse events leading to Adrenal crises (Safety analysis set)

Adverse events of unexpected therapeutic benefit (Safety analysis set)

*Repeat of AE Tables at episode level to be decided at Data Review meeting*

Signs and symptoms of adrenal insufficiency and over treatment (Safety analysis set)

Haematology (1) laboratory variables (Safety analysis set)

Change from baseline in Haematology (1) laboratory variables (Safety analysis set)

Shift table of baseline to minimum on-treatment for Haematology (1) laboratory variables (Safety analysis set)

Shift table of baseline to maximum on-treatment for Haematology (1) laboratory variables (Safety analysis set)

Haematology (1) results considered clinically significant by the investigator (Safety analysis set)

*Repeat above 5 tables for Haematology (2), Haematology (3)*

Biochemistry (1) laboratory variables (Safety analysis set)

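### Episode-level AE rates in SAP 11.2 count up to 30 post-treatment days for subjects who do not enter the extension, but the denominator stops at the last dose

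*SAP*

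**What the plan says.** SAP 11.2 sets two cut-offs for the AE summaries. Listed but not summarised is "any AE occurring after the last day of study treatment for subjects who enter the extension study"; the other cut-off is "the last day of study treatment plus 30 days for subjects who do not enter the extension study will be listed but not summarised". Extension entrants thus contribute no post-treatment days and everyone else contributes up to 30.

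The second group includes every early withdrawal. Protocol 11.1.9 states: "Subjects who discontinue from the study early are not eligible to take part in the extension study", and Protocol 11.5 repeats the rule. It also includes completers who decline. The data exist for these subjects: Protocol 12.2 collects AEs to the T4 call, about 30 days after the last or early-withdrawal visit, and the notes to Protocol Table 1 restrict that call: "Only for subjects who do not enter the extension study".

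SAP 11.2 then allows the AE summaries to be repeated as numbers of episodes, "using total number of patient-years exposed to IMP as the denominator". On when to do so it says: "This is optional and to be done only if there are differences in exposure between treatment groups", with the decision left to the Data Review Meeting. SAP Appendix A (14.1, Safety) already lists one episode-level overview table and leaves the other repeats to that meeting.

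SAP 11.1 defines a total duration (between first and last dose) and an actual duration (days with at least one dose). Neither contains post-treatment days. Protocol 12.5 treats the comparator as an IMP too, so the denominator works the same way in both arms.

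**The concern.** A rate per patient-year needs events and time from the same period. Here the numerator for a non-entrant runs up to 30 days past the end of the denominator. Nothing in the SAP adds those days to the exposure or limits the episode counts to on-treatment events.

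The purpose of these tables is to correct for unequal exposure between arms. Unequal withdrawal is one obvious cause of unequal exposure, and it also makes the mismatch differ between arms. The tables may therefore be called for in the situation where their own rate definition is least comparable. Extension entry is decided after randomisation in an open trial, so equal non-entry cannot be taken for granted. At stake is a descriptive safety comparison. The primary efficacy analysis is not touched.

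**Working it through.** **Plan's own figure.** The documents state no AE rate or person-time, so there is nothing to reproduce.

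**Inputs from the documents.** 120 randomised (SAP 5); 24-week treatment period (SAP 3); post-treatment window 0 or 30 days (SAP 11.2); denominator ends at last dose (SAP 11.1).

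**Assumptions, not in the documents.** 60 subjects per arm; 169 treatment days for a completer; withdrawal at day 84 (range day 28 to day 140); no completer declines unless stated; AE rate after stopping equal to *k* times the on-treatment rate, with *k* = 1 as base case and 0 to 2 as range. The non-entry percentages are illustrative. The plan's 15% is an inevaluability rate from all causes, not a withdrawal forecast.

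**Formula.** With *m* non-entrants and *D* total on-IMP days in an arm, the rate as defined divided by the true on-treatment rate is

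1 + *k* × 30*m* / *D*.

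**Base case (*k* = 1).**

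| Non-entry | *m* | *D* (days) | 30*m* | Inflation factor |
|---|---|---|---|---|
| 5% | 3 | 57×169 + 3×84 = 9,885 | 90 | 1.009 |
| 15% | 9 | 51×169 + 9×84 = 9,375 | 270 | 1.029 |
| 30% | 18 | 42×169 + 18×84 = 8,610 | 540 | 1.063 |

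**False between-arm ratio.**

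- 15% versus 5%: 1.0288 / 1.0091 = 1.020. Moving withdrawal from day 140 to day 28 gives 1.018 to 1.021.
- 30% versus 5%: 1.0627 / 1.0091 = 1.053. The same range of timing gives 1.047 to 1.061.
- If events are twice as frequent after stopping (*k* = 2): 1.04 and 1.11.
- If no events occur after stopping (*k* = 0), or if non-entry and its timing are equal in both arms: 1.00.

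**Is withdrawal the driver?** Take 10% withdrawals and no decliners in one arm: *D* = 54×169 + 6×84 = 9,630, and 180/9,630 gives 1.019. Take 5% withdrawals plus 15% decliners in the other: *D* = 9,885, *m* = 12, and 360/9,885 gives 1.036. The arm with fewer withdrawals is inflated more. The driver is total non-entry.

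**Do the subject-level percentages share the problem?** They have no time denominator. Under the plan a subject withdrawn at day 84 is observed for 84 + 30 = 114 days, against 169 for a completer who enters the extension. Cutting at the last dose would make this 84 against 169, which is less equal. Only subjects stopping after day 139 (139 + 30 = 169) get a longer window than that completer.

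**After the fix.** With on-treatment events only, the factor is 1.00 in each arm. With follow-up days added to the denominator and *k* = 1, the 15% arm gives (9,375 + 270) / (9,375 + 270) = 1.00. With *k* = 2 it gives (9,375 + 540) / 9,645 = 1.028, which is a correct rate over the whole period at risk.

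**The case against.** Four arguments on the other side have weight.

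- **Reach.** The main AE output is counts and percentages of subjects. The exposure-adjusted repeats are mostly optional and descriptive, and no AE hypothesis test is planned. This stands. One episode-level overview is nevertheless already in the table list, and being optional does not make the definition right when it is used.
- **Size.** If each arm had 100 to 300 episodes (an assumption) with Poisson counts, the 95% limits on a rate ratio would be a factor of about 1.32 to 1.17 either way, from exp(1.96 × √(2/n)). A 2% to 5% distortion is small beside that. This also stands. It limits the importance, but it does not justify a rate that is wrong by construction.
- **Design reason for the two windows.** Protocol 11.1.10 collects AEs arising between the studies through the extension's entry procedures for entrants, and by the T4 call only for non-entrants. The two cut-offs follow how the data are collected. This is a fair reason to keep them in the main tables, but it does not explain a denominator that omits the extra days.
- **Trigger.** Declining the extension after week 24 does not alter on-study exposure, so it would not itself call for these tables. The link between trigger and mismatch holds for withdrawals only.

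A reader might infer that the arm with more withdrawals will show inflated rates. The counter-case in the working shows that this need not follow, and the documents give no withdrawal or extension-entry figures by arm. A reader might also infer that the post-treatment days reflect a change of glucocorticoid. The documents do not say what non-entrants take afterwards, and comparator subjects were on their own prior therapy and need not change.

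**Conclusion.** The concern holds for the episode-level rates. As defined, they are inflated in proportion to each arm's non-entry to the extension whenever post-treatment events occur, and the ratio between arms is distorted if non-entry or its timing differs. Under the assumptions above the distortion is about 1.02 for 15% versus 5% non-entry and about 1.05 for 30% versus 5%. It is larger if events cluster after stopping and disappears if non-entry and its timing are balanced. The direction by arm is unknown.

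It is tempting to extend the criticism to the subject-level percentages because their windows also differ. The documents do not support a bias in a known direction there: for most early withdrawals the extra 30 days bring the window closer to a completer's. The window is longer than an entrant's only for completers who decline and for very late withdrawals.

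**What to change.** In SAP 11.2, require numerator and denominator to cover the same time in every episode-level table, including the overview listed in Appendix A. Either of two rules will do:

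1. Add each non-entrant's actual post-treatment follow-up days, up to 30, to the patient-years.
2. Count only events from first to last dose over IMP exposure, and show the post-treatment events of non-entrants separately.

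State which rule applies before treatment codes are seen. Leave the subject-level percentage tables as planned.

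The same edit should say whether exposure means the total or the actual duration of SAP 11.1. It should also correct the total-duration formula, which is printed as first dose date minus last dose date plus 1 and so gives zero or a negative number for any treatment lasting more than one day.

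The cost is minor SAP wording and programming, with one small additional table under rule 2. No new data are needed.
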